3.5.4. Electrocardiograms

Standard 12-lead ECG (including heart rate, PR, QT, QTcF intervals and QRS complex) will be obtained at times detailed in the schedule of activities given in the protocol. The average of the triplicate readings collected at each appropriate assessment time will be calculated for each ECG parameter, if applicable.

Change from time-matched baseline for heart rate, PR, QT, QTcF intervals and QRS complex will be calculated for each post baseline measurement. Baseline is defined as the time-matched value from the average of the triplicate recordings on Day -1.

In addition, the time-matched double difference in heart rate, PR, QT, QTcF and QRS measures is calculated in the following steps: (1) subtract predose value on Day 1 from all postdose values; (2) subtract the value at 0 hours on Day -1 from all other values on Day -1; (3) take the difference between the adjusted postdose value in (1) and its time-matched value in (2).

4. ANALYSIS SETS (POPULATIONS FOR ANALYSIS)

For purposes of analysis, the following analysis sets are defined:

Participant Analysis Set	Description
Enrolled/Randomly assigned to study intervention	"Enrolled" means a participant's, or their legally authorized representative's, agreement to participate in a clinical study following completion of the informed consent process. Potential participants who are screened for the purpose of determining eligibility for the study, but do not participate in

	the study, are not considered enrolled, unless otherwise specified by the protocol.
--	---

Defined Analysis Set	Description
PK Concentration Analysis Set	It is defined as all participants randomized and treated with PF-06882961 who have at least 1 plasma concentration value collected. The PK concentration analysis set will be used for plasma concentration summaries and plots.
PK Parameter Analysis Set	It is defined as all participants randomized and treated with PF-06882961 who have at least 1 of the PK parameters of interest. The PK parameter analysis set will be used for analyses on the PK parameters.
CCI	[REDACTED]
Safety Analysis Set (SAS)	It is defined as all participants who are randomized and receive at least one dose of study medications. The safety population will be used for the safety analyses.

Treatment Misallocations

All analyses will be performed on an “as-treated” basis and will not include data from participants who are randomized but not treated.

If a participant takes a treatment that is not consistent with the treatment they are randomized to, for example takes a treatment out of sequence or takes the same treatment twice, then they will be reported under the treatment that they actually receive for all safety and PK analyses, where applicable.

Protocol Deviations

Participants who experience events that may affect their PK profile (eg lack of compliance with dosing) may be excluded from the PK analysis. At the discretion of the pharmacokineticist a concentration value may also be excluded if the deviation in sampling time is of sufficient concern or if the concentration is anomalous for any other reason.

A full list of protocol deviations will be compiled and reviewed to identify potential important deviations and COVID-19 related deviations (if any) prior to database closure.

5. GENERAL METHODOLOGY AND CONVENTIONS

The study data will be analyzed following the database release once all participants have completed the study (or discontinued from study).

5.1. Hypotheses and Decision Rules

None.

5.2. General Methods

In general, PF-06882961 plasma PK concentration and parameters data will be summarized descriptively for single dose and multiple doses separately; safety endpoints will be summarized by treatment group and dose levels; **CCI**

5.2.1. Analyses for PK Concentration and Parameters

Concentration data will be listed and summarized descriptively by PK sampling time and day (dose level). Summary profiles (mean and median) of the plasma concentration-time data will be plotted by day (dose level) against nominal PK sampling time. Mean and median profiles will be presented on both linear-linear and loglinear scales. Spaghetti plots of individual plasma concentration-time data will be plotted by day (dose level) and actual PK sampling time.

The primary endpoints AUC_{24} , C_{max} , $C_{max,ss}$, **CCI** will be summarized descriptively with n, arithmetic mean, standard deviation, coefficient of variation (CV%), geometric mean, geometric CV (%), median, minimum, and maximum. Box and whisker plot of individual and geometric mean will be presented for dose normalized AUC_{24} , C_{max} , $C_{max,ss}$.

5.2.2. Analyses for Continuous Endpoints

Continuous endpoints will be summarized descriptively by treatment, dose level and day (if collected multiple days for same dose level) with summary statistics of n, mean, standard deviation, median, minimum, and maximum.

CCI

CCI

CCI

5.2.3. Analyses for Categorical Endpoints

Categorical endpoints will be summarized descriptively by treatment, dose level and day (if collected multiple days for same dose level) with n, number of observed values, and percentages.

5.3. Methods to Manage Missing Data

For the analysis of safety endpoints, the CDISC and Pfizer Standard (CaPS) rules for imputation will be applied.

5.3.1. Concentrations Below the Limit of Quantification

In all data presentations (except listings), concentrations below the limit of quantification (BLQ) will be set to zero. (In listings BLQ values will be reported as “<LLQ”, where LLQ will be replaced with the value for the lower limit of quantification.)

5.3.2. Deviations, Missing Concentrations and Anomalous Values

In summary tables and plots of median profiles, statistics will be calculated having set concentrations to missing if 1 of the following cases is true:

1. A concentration has been collected as ND (ie not done) or NS (ie no sample),
2. A deviation in sampling time is of sufficient concern or a concentration has been flagged anomalous by the pharmacokineticist.

Note that summary statistics will not be presented at a particular time point if more than 50% of the data are missing.

5.3.3. Pharmacokinetic Parameters

Actual PK sampling times will be used in the derivation of PK parameters.

If a PK parameter cannot be derived from a participant's concentration data, the parameter will be coded as NC (ie not calculated). (Note that NC values will not be generated beyond the day that a participant discontinues.)

In summary tables, statistics will be calculated by setting NC values to missing; and statistics will be presented for a particular treatment with ≥ 3 evaluable measurements. For statistical analyses (ie ANOVA), PK parameters coded as NC will also be set to missing; and analyses will not be performed for a particular parameter if more than 50% of the data are NC.

If an individual participant has a known biased estimate of a PK parameter (due for example to an unexpected event such as vomiting before all the compound is adequately absorbed in the body), this will be footnoted in summary tables and will not be included in the calculation of summary statistics or statistical analyses.

CCI

6. ANALYSES AND SUMMARIES

6.1. Primary Endpoint(s)

The primary endpoints, AUC_{24} (Day 1 and Steady State), C_{max} (D1), $C_{max,ss}$, will be summarized descriptively as described in Section 5.2.1.

In addition, to support the assessment of primary endpoints, AUC_{tau1} (Steady State), AUC_{tau2} (Steady State), C_{max1} (Steady State), C_{max2} (Steady State), $AUC_{tau1}(dn)$ (Steady State), $AUC_{tau2}(dn)$ (Steady State), $AUC_{24}(dn)$ (Day 1 and Steady State), $C_{max1}(dn)$, $C_{max2}(dn)$, $C_{max}(dn)$, $C_{max,ss}(dn)$ will also be summarized descriptively. Box and whisker plots will be generated for $AUC_{24}(dn)$ (Day 1 and Steady State), $C_{max}(dn)(D1)$, $C_{max,ss}(dn)$. See **Table 3**.

The PK parameter analysis set will be used for the aforementioned summaries and plots.

Table 3. Descriptive Summaries for Primary PK Parameters Following the Single Dose/Multiple Doses

Summarized by Dose Level	
Parameter	Summary Statistics
AUC_{24} (D1 and SS), C_{max} (D1), $C_{max,ss}$	
AUC_{tau1} (SS), AUC_{tau2} (SS), C_{max1} (SS), C_{max2} (SS)	
$AUC_{tau1}(dn)$ (SS), $AUC_{tau2}(dn)$ (SS), $AUC_{24}(dn)$ (D1 and SS), $C_{max1}(dn)$ (SS), $C_{max2}(dn)$ (SS), $C_{max}(dn)$ (D1), $C_{max,ss}(dn)$	N, arithmetic mean, median, cv%, standard deviation, minimum, maximum, geometric mean and geometric cv%.

D1=Day 1. SS=Steady Status. dn= Dose Normalized value. cv=Coefficient of Variation.

Presentations for PF-06882961 concentrations will be generated for the single dose and multiple doses separately, including:

- A listing of all concentrations sorted by participant ID and nominal time postdose, and page by dose level for multiple dosing days. The concentration listing will also include the actual times. Deviations from the nominal time will be given in a separate listing.

- A summary of concentrations by dose level and nominal time postdose, where the set of statistics will include n, mean, median, standard deviation, cv, minimum, maximum and the number of concentrations above the lower limit of quantification.
- Median concentrations time plots (on both linear and semi-log scales) against nominal time postdose by dose levels (all dose levels on the same plot per scale for multiple dosing days) based on the summary of concentrations by dose level and nominal time postdose.
- Median concentrations time plots (on both linear and semi-log scales) against nominal time postdose by dose levels (all dose levels on the same plot per scale for multiple dosing days) based on the summary of concentrations by dose level and nominal time postdose.
- Individual concentration time plots by dose (on both linear and semi-log scales) against actual time postdose (there will be separate spaghetti plots for the single dose and each multiple dose level per scale).
- Individual concentration time plots by participant (on both linear and semi-log scales) and dose level against actual time postdose (there will be separate plots for each participant on single dose, and separate plots for each participant with all dose levels on the same plot per scale).

For summary statistics and median/mean plots by sampling time, the nominal PK sampling time will be used. For individual participant plots by time, the actual PK sampling time will be used. The PK concentration analysis set will be used for all the concentration data summaries and plots.

6.2. Secondary Endpoint(s)

The secondary safety endpoints will be summarized using the safety analysis set as described in Sections 5.2.2 and 5.2.3, and analyses for each safety endpoint are described in Section 6.6.

CCI

6.4. Subset Analyses

None.

6.5. Baseline and Other Summaries and Analyses

6.5.1. Baseline Summaries

Demographic and baseline characteristics (age, gender, race, ethnicity, weight, height, body mass index and duration of diabetes) collected prior to the first dose of the study intervention will be summarized by treatment group following the CaPS.

6.5.2. Study Conduct and Participant Disposition

Participant disposition will be reported by showing the number (and percent) of participants completed study, discontinued from studies, as well as the number (and percent) of participants analyzed for each analysis set by treatment group.

6.5.3. Concomitant Medications and Nondrug Treatments

All concomitant medications as well as nondrug treatments will be provided in the listings.

A separate listing restricted to metformin will also be produced.

6.5.4. Treatment Compliance

A summary table of treatment compliance will be produced by study week according to current sponsor reporting standards.

“Study Week” will be calculated using actual visit dates per dose titration dates, rather than the calendar days. For example, if dose missing occurs on Day 8 and dose titration occurs on Day 9 for a given patient, then the dose missing is considered to have occurred on Week 1 for this patient (Week 1 is Day1 to Day 8 for this patient).

6.5.5. COVID-19 Related Analyses

Considering the small sample size in this study, no separate summary tables are planned for COVID-19 related analyses. Only some key listings will be provided. e.g.,

Protocol Deviations related to COVID-19,

Subject Discontinuations Related to COVID-19,

COVID-19 related Adverse Events.

6.6. Safety Summaries and Analyses

Safety data will be presented in tabular and/or graphical format and summarized descriptively according to the CaPS.

6.6.1. Adverse Events

Adverse events will be reported in accordance with the CaPS by treatment group and dose level.

Besides the standard incidence and severity of TEAE summaries, the number of TEAEs (all causality and treatment related) by severity, System Organ Class, and Preferred Term will also be produced.

The hypoglycemic AEs will be listed in a separate table and summarized categorically (See Section 3.5.1.1) by treatment and dose level.

CCI

CCI

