### 4.2. Scientific Rationale for Study Design

The purpose of this study is to evaluate the PK, safety and tolerability of single and multiple oral doses of PF-06882961 in adult Chinese participants with T2DM who are receiving metformin as background antihyperglycemic medication. **CCI**

CCI [REDACTED] Results from this study will be compared with Global studies (C3421002 and C3421005) to facilitate the analyses of ethnic differences in PK, CCI [REDACTED] and tolerability between Chinese and Westerners.

Completed studies indicated that PF-06882961 exposures in T2DM participants was 1.7-fold higher than that in healthy participants, despite higher body weight. In Study C3421002, the steady-state PK of PF-06882961 was characterized in a T2DM population. A similar Chinese population with T2DM was selected in the current study to facilitate the PK comparison of PF-06882961 between Chinese and Western participants. CCI [REDACTED]

[REDACTED]

Based on the results from Study C3421002, the starting dose of PF-06882961 in the current study will be set at 10 mg BID (or matching placebo). The dose will then be up-titrated approximately weekly to reach the target level of 120 mg BID at Week 7. Such dose titration was adopted to enhance the tolerability to higher doses of PF-06882961. This titration scheme is identical to that in Global Study C3421005 which permits the comparison of tolerability between Chinese and Westerners. It is considered that gastrointestinal adverse events common to GLP-1R agonists are mostly expected soon after dose increases. Therefore, the 2-week maintenance period of 120 mg BID (Visits 8-10) is sufficient to characterize the safety and tolerability of PF-06882961 in the current China Phase 1 study. Such titration and maintenance period is identical to part of that in Study C3421005 which allows a comparison CCI [REDACTED] after 8-week treatment, CCI [REDACTED]. The data will also be pooled with a number of other studies and assessed via population PK and PK CCI [REDACTED] analyses. CCI [REDACTED] safety data obtained in Chinese participants will be compared with data from Study C3421005 in which similar titration and maintenance schedules were adopted.

A baseline day (Day -1) with time-matched procedures will permit an improved assessment of safety, tolerability, CCI [REDACTED]. The participants and site staff will be blinded to administration of active versus placebo to permit an unbiased assessment of tolerability and safety.

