### 4.3. Justification for Dose

In this study, PF-06882961 will be administered BID in titration: starting with 10 mg and titrated approximately weekly up to 120 mg within 6 weeks, followed by 2-week maintenance at 120 mg. It is considered that steady state is achieved during each weekly titration step. The PF-06882961 doses selected for this study are based on observed safety, tolerability, PK, CCI data from the completed 4-week study comparing PF-06882961 to placebo in T2DM participants (Study C3421002); as well as the exposure margins relative to observed toxicology findings. Exposure margins for the proposed dose in this study (120 mg BID) are given in Section 2.2.1.3.

Doses ranging from 10 mg BID to 120 mg BID were generally safe and well tolerated in Phase 1 Study C3421002. The titration scheme used in this study is slower than that used in C3421002. CCI [REDACTED]. Given the current dose titration and PK sampling schedule,  $AUC_{24}$  and  $C_{max}$  parameters from the 40 mg and 80 mg doses will be determined.

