3.5. Safety Endpoints

3.5.1. Adverse Events (AEs)

An adverse event is considered a Treatment-Emergent Adverse Event (TEAE) if the event started during the effective duration of treatment.

All events that start on or after the first dosing day and time/start time, if collected, but before the last dose plus the lag time will be flagged as TEAEs. If an AE starts on the same day as the first dose date, it will be considered treatment emergent unless the case report form data indicates otherwise via explicitly recording time for AE onset and treatment dosing.

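### Do the dose-level adverse event tables mislead because 120 mg is taken for two weeks and each lower step for about one?

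*SAP*

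**What the plan says.** SAP 6.6.1 sets the layout: "Adverse events will be reported in accordance with the CaPS by treatment group and dose level". Besides the standard incidence and severity summaries, it adds that "the number of TEAEs (all causality and treatment related) by severity, System Organ Class, and Preferred Term will also be produced". SAP 6.2 says that "The secondary safety endpoints will be summarized using the safety analysis set as described in Sections 5.2.2 and 5.2.3", and 5.2.3 ends its rule for categorical endpoints with "if collected multiple days for same dose level) with n, number of observed values, and percentages".

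On timing, Protocol 4.3 has the dose "titrated approximately weekly up to 120 mg within 6 weeks, followed by 2-week maintenance at 120 mg". Protocol 4.2 explains why two weeks at the top dose are considered enough: "gastrointestinal adverse events common to GLP-1R agonists are mostly expected soon after dose increases".

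SAP 3.5.1 extends the treatment-emergent window beyond dosing: events on or after the first dose "but before the last dose plus the lag time will be flagged as TEAEs". The visible text does not give the lag. For compliance only, SAP 6.5.4 says that study week "will be calculated using actual visit dates per dose titration dates, rather than the calendar days".

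SAP 6.6 and 6.6.1 both defer to CaPS, the sponsor's reporting standard, and part of 6.6.1 is redacted. The SAP version history says that summaries for adverse events of interest were added to 6.6.1. None is visible there, so the redaction does cover some adverse event analyses.

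**The concern.** A table with one column per dose level invites the reader to look across the columns for a dose trend. Here the last column covers twice the time of each other column, so an event with no relation to dose would still appear more often at 120 mg. Raw event counts also depend on how many participants reached each level. The treatment-emergent window runs past the last dose, and a completer's last dose is 120 mg. If events from the lag were placed in that column, its excess would grow.

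Safety and tolerability are the secondary objective, and 120 mg BID is the target dose. A spurious rise in that column could be read as poorer tolerability at the dose of most interest.

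**Working it through.** **Days at each level.** Protocol 6.1 lists seven dose levels. The titration figure is not shown, so the step starts are inferred from the weekly visit days: Days 1, 8, 15, 22, 29, 36 and 43, with the last dose on Day 56. Then 6 × 7 + 14 = 56 days, which reproduces the stated 8 weeks. This map puts 40, 80 and 120 mg on Days 21, 35 and 56, in agreement with the intensive PK days and the doses named in the primary endpoints.

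**Event counts at a constant rate.** Per participant who reaches the level, the ratio is 14/7 = 2.0. For raw counts it is 2.0 if all 15 active participants complete 120 mg. If only the planned minimum of 8 do so, it is (8 × 2)/(15 × 1) = 1.07. Protocol 9.2 gives the 8 as a minimum of evaluable completers, not as a forecast.

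**Percentage with an event.** Let h be the weekly hazard in the first week at a level, p = 1 − exp(−h) the 7-day risk, and r the second-week rate at 120 mg as a fraction of the first. Then

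ratio = [1 − exp(−h(1 + r))] / [1 − exp(−h)], which equals 2 − p when r = 1.

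The prior-study figures come from Protocol 2.2.2.1. They pool arms and doses, and the period over which they are spread is an assumption.

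| Case | h | r | 7-day risk | Risk at 120 mg | Ratio | Excess of 15 |
|---|---|---|---|---|---|---|
| Assumed 30% risk over 8 weeks | 0.0446 | 1 | 4.4% | 8.5% | 1.96 | 0.63 |
| Headache, 23.5% taken as a 28-day risk | 0.0670 | 1 | 6.5% | 12.5% | 1.94 | 0.91 |
| Any TEAE, 319/98 = 3.26 over 4 weeks | 0.814 | 1 | 55.7% | 80.4% | 1.44 | 3.7 |
| Any TEAE, 3.26 over 8 weeks | 0.407 | 1 | 33.4% | 55.7% | 1.67 | 3.3 |
| Any TEAE, over 4 weeks | 0.814 | 0.25 | 55.7% | 63.8% | 1.15 | 1.2 |
| Any TEAE, over 8 weeks | 0.407 | 0.25 | 33.4% | 39.9% | 1.19 | 1.0 |

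**Which rows apply.** Five of the six most frequent TEAEs in the earlier study were gastrointestinal: nausea, dyspepsia, vomiting, diarrhea and constipation. Protocol 4.2 expects such events early after each increase, so r lies well below 1 for them. At h = 0.0446, r = 0 gives 1.00 and r = 0.25 gives 1.24. Gastrointestinal events also dominate the any-TEAE row, so its last two lines fit the documents better than its constant-rate lines.

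**What a rate per participant-week would do.** For the same first-week burden, the 120 mg rate divided by the lower-step rate is (1 + r)/2. With r between 0 and 0.25 this is 0.50 to 0.63. For early-onset events the adjusted figure therefore understates 120 mg by more than the plain percentage overstates it.

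**Lag.** If lag events were assigned to 120 mg at the on-treatment rate, the count ratio would be (14 + lag)/7, or 42/7 = 6.0 for an assumed 28-day lag. The protocol gives a half-life of about 4.7 to 8.1 hours, so five half-lives end within about 5 × 8.1 = 40.5 hours. An undiminished drug-related rate over 28 days is therefore not a realistic case.

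**The case for a change.** The best case for a change is that it would cost almost nothing. Titration dates are already used for compliance, so a header line with participant-weeks, or a split of 120 mg into its first and second week, needs no new data. Readers will focus on the 120 mg column. The lag and attribution rule matters however gastrointestinal events are timed. Protocol Table 3 also lists placebo as a single level. If it were shown as one column, it would span 56 days beside 7-day active columns.

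Some of this stands. The visible text does not give the lag, the denominator per level or the attribution rule, and a table that showed time at each level would be slightly easier to read. But these are conventions that a sponsor adverse event standard would be expected to hold. SAP 6.6.1 invokes that standard, so their absence from the visible text does not show that they are absent from the plan.

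Participant-time would not make the levels comparable either. Every active participant takes the doses in the same ascending order, so dose is tied to sequence, adaptation and dropout whatever the denominator. The comparison that randomization supports, active against placebo over the same period, has equal planned time in both arms. Step lengths are stated in the protocol, so a reader can see that 120 mg lasts two weeks.

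**Conclusion.** No change follows. The durations do differ, by 14 days to about 7, but the factor of 2.0 is for events per participant at a constant rate, a measure the visible SAP text does not name. For the tabulated percentages, the ratio is about 1.0 to 1.24 for a gastrointestinal term with early onset. It reaches about 1.9 for a single term that can start on any day, where the excess is under one participant of 15. No test, estimate or stated conclusion depends on it, and the overall by-treatment table is unaffected.

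The remedies bring little. Events per participant-week would distort the commonest events in the other direction, and a header line or week split only restates design facts in a descriptive table. The missing rules are details that analysts will settle from the reporting standard.

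This rests on step lengths inferred from the visit days, on gastrointestinal events falling mostly in the first week after an increase, and on prior-study frequencies used only as an assumed level. With ±1-day visit windows, an individual's own time ratio can run from 12/9 = 1.33 to 16/5 = 3.2.
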